2.3.2 Benefit Assessment

There are currently no approved treatments that are specifically targeted towards sleep disturbances associated with menopause although sleep disturbances are one of the most common and debilitating symptoms experienced by women in the menopausal period. The dual mechanism of elinzanetant acting congruently on the 2 main symptoms of menopause, VMS and sleep disturbances can be a significant addition to the treatment options available to healthcare professionals and patients.

Based on the mode of action, preclinical, and clinical data it is expected that treatment with elinzanetant will provide relevant clinical benefits to menopausal women with sleep disturbances. These benefits may include, but are not limited to:

Reduction of wakefulness after sleep onset

Improvements in sleep efficiency

Improvements in sleep quality

Participants who are randomized to placebo are still expected to have some benefit from participation in the study as they will receive a thorough medical evaluation.

2.3.3 Overall Benefit: Risk Conclusion

Taking into account the measures taken to minimize risk to participants in this study, the potential risks identified in association with elinzanetant are justified by the anticipated benefits that may be afforded to participants with sleep disturbances associated with menopause.

3. Objectives, Endpoints, and Estimands

Objectives and endpoints are listed in Table 3–1.

21 SEP 2023 Page: 21 of 73

Table 3-1: Objectives and endpoints

Objectives Endpoints			
Primary	Liiupoiiits		
To explore the efficacy of elinzanetant on sleep disturbances associated with menopause as determined by PSG	Primary endpoint Change from baseline in WASO at Week 4 as measured by PSG Secondary endpoints Change from baseline in WASO at Week 12 as measured by PSG Change from baseline in SE at Week 4 as measured by PSG Change from baseline in SE at Week 12 as measured by PSG		
Secondary	, -		
To explore the efficacy of elinzanetant on sleep disturbance associated with menopause as determined by patient- reported outcomes	 Change from baseline in PROMIS SD SF 8b total score at Week 4 Change from baseline in PROMIS SD SF 8b total score at Week 12 Change from baseline in ISI total score at Week 4 Change from baseline in ISI total score at Week 12 		
To evaluate the safety of elinzanetant	TEAEs		
for the treatment of sleep disturbances associated with menopause	Abnormal laboratory parameters		
Exploratory			
To explore the relationship between HF and sleep disturbances as determined by PSG	 Frequency of HFs over time WASO as measured by PSG over time 		
To explore the efficacy of elinzanetant on the frequency of anxiety symptoms	Change from baseline in GAD-7 total score over time		
To evaluate the efficacy of elinzanetant on the PGI-S and PGI-C	 Actual values of the PGI-C individual item scores over time Change from baseline in PGI-S individual item scores over time 		
Other pre-specified			
To evaluate variability in exposure in relation to the efficacy and safety for elinzanetant	Systemic exposure of elinzanetant in plasma via sparse PK sampling		
To further investigate the study intervention and similar compounds (e.g., mode-of-action-related effects, safety) and to further investigate pathomechanisms deemed relevant to sleep disturbances associated with menopause.	 Various biomarkers (e.g., diagnostic, safety, pharmacodynamic, monitoring, or potentially predictive biomarkers) 		
 To investigate the efficacy of elinzanetant on sleep disturbance associated with menopause determined by Sleepiz One+ 	 Parameters captured remotely and continuously at home by Sleepiz One+ including e.g. WASO, TST, SE 		

The full list of exploratory endpoints will be presented in the SAP.

GAD-7 = General Anxiety Disorder-7, HF = Hot Flash, ISI = Insomnia Severity Index, PGI-C = Patient Global Impression of Change, PGI-S = Patient Global Impression of Severity, PK = Pharmacokinetics, PROMIS SD SF 8b = Patient-Reported Outcomes Measurement Information System Sleep Disturbance Short Form 8b, PSG = Polysomnography, SAP = Statistical analysis plan, SE = Sleep Efficiency, TEAE = Treatment-emergent adverse event, TST = Total Sleep Time,

21 SEP 2023 Page: 22 of 73

WASO = Wakefulness after sleep onset.

Estimands

The primary clinical question of interest for the primary objective is:

What is the difference in mean change from baseline in WASO as measured by PSG at Week 4 comparing elinzanetant to placebo in women with sleep disturbances associated with menopause assuming no study treatment interruption and discontinuation and no use of prohibited concomitant medications impacting sleep?

The attributes of the main estimand for the primary endpoint are as follows:

- Population: Women aged 40–65 with sleep disturbance associated with the menopause, further defined by the key inclusion/exclusion criteria.
- Variable: Change from baseline in WASO measured by PSG at Week 4.
- Treatment: Elinzanetant 120 mg or placebo.
- ICEs and strategies: Important ICEs to consider are listed in Table 3–2.

Table 3-2: Primary Estimand: ICEs and Strategies to Address Them

ICEs	Proposed Strategy	Data Handling Method	Interpretation
Temporary study treatment interruption	Hypothetical	Discard data collected after the ICE	The treatment effect that would be if participants complied with treatment
Premature discontinuation of study treatment	Hypothetical	Discard data collected after the ICE	The treatment effect that would be if participants did not discontinue the randomized treatment
Intake of prohibited concomitant medication having impact on efficacy	Hypothetical	Discard data collected after the ICE	The treatment effect that would be if participants did not take prohibited concomitant medications impacting sleep

ICE = Intercurrent event.

 Population level summary: Mean change from baseline in WASO measured by PSG at Week 4.

4. Study Design

4.1 Overall Design

This is a multi-center, multi-country, double-blind, randomized, parallel-group, placebo-controlled, pilot intervention study in women with sleep disturbances associated with the menopause.

21 SEP 2023 Page: 23 of 73

Screening: After giving informed consent, participants will be withdrawn from prohibited concomitant medications (see Section 10.7) at SCR-1 visit if needed. Screening period consists of 3 visits.

Randomization: At the end of the screening period (BL visit), the participants will be randomized into elinzanetant and placebo arms in a 1:1 ratio. Randomization will be stratified by the average weekly frequency of moderate to severe HFs (including night-time HFs) over the 14 days prior to the respective eligibility check (<35 moderate to severe HFs per week, ≥35–<50 moderate to severe HFs per week).

Intervention period: Intervention period will last about 12 weeks:

• 120 mg (2x 60 mg soft gel capsules) of elinzanetant or matching placebo orally once daily for 12 weeks

Follow-up: The intervention period will be followed by a 4-week safety follow-up period.

The study includes 3 stationary visits in a sleep laboratory. Each of these visits encompasses 2 consecutive nights. This results in a total of 6 nights in the sleep laboratory.

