- 13. Travel across \geq 3 time zones within 2 weeks prior to the SCR-2 visit, or planned travel across \geq 3 time zones during study.
- 14. Regular napping i.e. >3 naps per week each with duration of >30 minutes.
- 15. At screening a suicidal ideation in the past 6 months (as indicated by "Yes" on item 4 or item 5 of the suicidal ideation section of the eC-SSRS) or suicidal behavior in the past 6 months (indicated by "Yes" on any item of the suicidal behavior section of the eC-SSRS).
- 16. Clinically relevant drug or alcohol abuse within 12 months of signing of informed consent.
- 17. Use of substances that in the opinion of the investigator contribute to the participant's sleep disturbances (e.g. caffeine, alcohol, cannabis and its derivatives).
- 18. Dependent on the investigator, the contract research organisation(s) or Sponsor for education or employment (e.g. family members, employees, people who receive grants/education).
- 19. Known hypersensitivity to elinzanetant or any of the excipients in the formulation.
- 20. Inability to comply with the study procedures for any reason, including the following examples: language comprehension, psychiatric illness, general inability to get to the study site or ePRO completion.

Additional criteria

21. Current diagnosis of the following pre-malignant conditions: cervical dysplasia; breast atypia including atypical ductal hyperplasia, atypical lobular hyperplasia, lobular carcinoma in situ; cirrhosis of the liver; and nodular hepatic lesions.

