5.5 Criteria for Temporarily Delaying Randomization

If a participant is otherwise eligible, acute intercurrent conditions (e.g. current febrile illness, quarantine for suspicion of COVID-19) may allow to postpone start of study medication in a participant to a time when the condition has resolved.

A delayed assessment or report of procedures required for assessment of eligibility would constitute a reason for postponing randomization.

Under these circumstances, the screening period may be extended until these conditions have resolved or the delayed assessment is available. In case the screening period is extended to more than 8 weeks, a new blood sample has to be taken and urinalysis as well as a urine pregnancy test need to be performed for assessment of eligibility.

6. Study Intervention(s) and Concomitant Therapy

Study interventions are all pre-specified, investigational and non-investigational medicinal products, medical devices and other interventions (e.g., surgical and behavioral) intended to be administered to the study participants during the study conduct.

21 SEP 2023 Page: 29 of 73

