8.3.5 Suicidal Ideation and Behavior: Electronic Columbia-Suicide Severity Rating Scale (eC-SSRS)

Suicidal ideation and behavior will be monitored by eC-SSRS questionnaire. Use of the eC-SSRS is required by the US FDA in clinical trials of new compounds with a central mode of action.

The eC-SSRS is a fully structured participant rated questionnaire designed and developed for computer administration. Participants respond to standardized clinical questions presented in a uniform fashion and adhering to the original C-SSRS clinical conventions. The eC-SSRS assesses lifetime suicidality during an initial baseline evaluation, and then prospectively monitors ideations and behaviors at subsequent follow-up assessments. The eC-SSRS assesses the severity and frequency of suicidal ideation and behavior. The information collected in the eC-SSRS is classified into a set of 11 categories for suicidal ideation and suicidal behavior, and self-injurious behavior without suicidal intent.

See Exclusion Criteria 15 for information on when the participant should not be randomized based on suicidal behavior or ideation.

• The investigator will receive an email notification if a participant has a "Yes" score on item 4 or item 5 of the suicidal ideation section of the eC-SSRS or "Yes" on any item of the suicidal behavior section. If this happens after randomization, the participant can continue the study at the discretion of the investigator. The investigator has to report this as an adverse event. In addition, any suicidal ideation and/or behavior should be treated according to local clinical practice.

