8.4.1 Time Period and Frequency for Collecting AE and SAE Information

(S)AEs will be collected from the start of study intervention until the last follow-up visit at the timepoints specified in the SoA (Section 1.3). (S)AEs which are related to protocol-required study procedures (e.g., (S)AE related to invasive study procedures) will be recorded as (S)AEs from the signing of the ICF.

21 SEP 2023 Page: 44 of 73

Any medical occurrences/conditions that begin in the period between signing ICF and the start of study intervention, and which are not related to a protocol-required study procedure, will be recorded as medical history/current medical conditions, not as (S)AEs.

All SAEs will be recorded and reported to the Sponsor or designee immediately and under no circumstance should this exceed 24 hours of learning of the event, as indicated in Section 10.3. The investigator will submit any updated SAE data to the Sponsor within 24 hours of it being available.

Investigators are not obligated to actively seek information on AEs or SAEs after conclusion of the study participation. However, if the investigator learns of any SAE, including a death, at any time after a participant has been discharged from the study, and the investigator considers the event to be reasonably related to the study intervention or study participation, the investigator must promptly notify the Sponsor.

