At least 2 weeks or 5 half-lives (whichever is longer) prior to SCR-2 visit	 Antidepressant drugs Anticonvulsants Antipsychotics (for depot neuroleptics consider long half-lives) Anxiolytics (benzodiazepines, non-benzodiazepines) Hypnotics Centrally acting anticholinergics Mood stabilizers Muscle relaxants (centrally acting with psychotropic effects) Central Alpha-2 Receptor Agonists Sodium oxybate Sedating antihistamines Melatonin and melatonin receptor agonists Stimulants Adenosine Receptor Antagonist Systemic corticosteroids (inhaled corticosteroids are allowed) Diet pills that contain active substance and/or ingredients that can affect sleep Isotretinoin Any recreational drugs, even if used for medicinal reasons Opioids/narcotics Over-the-counter (OTC) /herbal treatments including: Supplements with possible psychotropic effect Extended-release pseudoephedrine Traditional Chinese medicine used for sleep improvement/disturbances 	
PSG = polysomnography, S0	CR = Screening.	

21 SEP 2023 Page: 70 of 73

Table 10-5: Medication with limited use during the study

During the study	Therapies
Allowed up to twice per week	 Non-sedating antihistamines. See Table 10–6 for non- sedating antihistamines which are prohibited during the study as CYP3A4 substrates.
	Pseudoephedrine

CYP3A4 = Cytochrome P450 isoenzyme 3A4.

Table 10-6: Prohibited concomitant medication potentially affecting PK.

Washout period before SCR-2	Therapies
At least 2 weeks or 5 half-lives (whichever is longer) prior to SCR-2 visit: CYP3A4 substrates with a narrow therapeutic range	Alfentanil, astemizole, fentanyl, pimozide, terfenadine
At least 2 weeks or 5 half-lives (whichever is longer) prior to SCR-2 visit: Strong or moderate inhibitors of CYP3A4	Nefazodone, fluvoxamine, tofisopam
At least 2 weeks or 5 half-lives (whichever is longer) prior to SCR-2 visit: Strong or moderate inducers of CYP3A4	Carbamazepine, phenytoin, St. John's wort, phenobarbital, primidone
Washout period before BL	Therapies
From 1 week prior to BL visit: CYP3A4 substrates with a narrow therapeutic range	Cisapride, cyclosporine, dihydroergotamine, ergotamine, quinidine, sirolimus, tacrolimus
From 2 weeks prior to BL visit: Strong or moderate inhibitors of CYP3A4	See Table 10–7 for examples of most common moderate and strong CYP3A4 inhibitors
From 4 weeks prior to BL visit: Strong or moderate inducers of CYP3A4	See Table 10–8 for examples of most common moderate and strong CYP3A4 inducers

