4.1.1.4 Adverse Events (AE) and Concomitant Medications (CM)

For computation of durations, i.e., time between start and end dates of certain events and concomitant medication intake, a complete date is necessary.

The following rule will be applied to impute partial missing start or end date of AE/CM:

An imputation range will be defined as the earliest possible date (lower range) and the latest possible date (upper range) of the occurrence of AE/CM. If AE/CM end date is available, this will be used as the latest possible AE/CM occurrence date in the imputation range.

If the start of study treatment date falls within imputation range, incomplete AE/CM start date will be imputed as the start of study treatment date. Otherwise, the partially missing AE/CM start date will be imputed to the earliest date of the imputation range. Completely missing start date will not be imputed and will be considered treatment-emergent for AEs and concomitant for CMs.

Partially missing AE/CM end date will be imputed as the latest possible date of AE/CM imputation range. Completely missing end date will not be imputed and presumed to be ongoing.

Version 2.0 Page: 17 of 57

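### For women withdrawn from psychotropics at SCR-1, no new eC-SSRS is scheduled before randomization to inform exclusion 15

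*Protocol*

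**What the plan says.** **Withdrawal.** Protocol Section 4.1 states that, after consent, "participants will be withdrawn from prohibited concomitant medications (see Section 10.7) at SCR-1 visit if needed". Table 10-4 in Section 10.7 lists "Antidepressant drugs" along with antipsychotics, mood stabilizers, anticonvulsants, anxiolytics and hypnotics. These must be stopped at least 2 weeks or 5 half-lives before SCR-2, whichever is longer. For chronic anxiolytic or hypnotic use the minimum is 4 weeks.

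**Eligibility.** Exclusion 15 (Section 5.2) covers "At screening a suicidal ideation in the past 6 months", or suicidal behaviour in the same period, as answered on the eC-SSRS. Section 8.3.5 points to this criterion as the rule on when not to randomize for suicidality. It adds that use of the instrument "is required by the US FDA in clinical trials of new compounds with a central mode of action".

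**Schedule.** In Table 1-2 the eC-SSRS is marked at SCR-1, T1 (Week 4) and T3/EoT; SCR-2 and BL are blank. The inclusion/exclusion row is marked at all three screening visits. If screening runs past 8 weeks, Section 5.5 requires that "a new blood sample has to be taken and urinalysis as well as a urine pregnancy test need to be performed"; the eC-SSRS is not among the repeats.

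**Reporting.** For a positive form, Section 8.3.5 says "If this happens after randomization, the participant can continue the study at the discretion of the investigator", and an AE report is then required. For conditions that begin between consent and first dose, Section 8.4.1 says that those "which are not related to a protocol-required study procedure, will be recorded as medical history/current medical conditions, not as (S)AEs".

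**Analysis.** SAP 4.5.3.4 summarizes the eC-SSRS by treatment at baseline, week 4 and week 12. SAP 4.5.3 counts participants whose laboratory, liver or vital-sign baseline was taken while using or washing out a prohibited drug. It does not name the eC-SSRS.

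**The concern.** Stopping an antidepressant, mood stabilizer or antipsychotic is a change after which an investigator would want to ask about suicidality again. The protocol directs that change at SCR-1 and then schedules no eC-SSRS until four weeks into double-blind treatment. A woman who develops ideation during washout could be randomized, to placebo or to a centrally acting drug, with exclusion 15 judged on answers she gave before the drug was stopped.

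The plan shows awareness of the same timing problem elsewhere. The SAP limits the PROMIS, ISI, GAD-7, PGI-S, sleep-diary and hot-flash baselines to time outside the impact of prohibited drugs, and it counts affected laboratory, liver and vital-sign baselines. Section 5.5 accepts that screening results go stale after 8 weeks. The eC-SSRS has none of these provisions, and the documents give no reason for leaving it out.

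A smaller matter is interpretation. When a Week 4 form is positive in a woman who was washed out, there is no form after the withdrawal and before the first dose with which to compare it.

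**Working it through.** The plan gives no figure on this point, so there is none to reproduce. The check is a reading of the schedule and a count of days.

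**Step 1: read the schedule by column.** The ISI row (SCR-1, BL, T1, T3/EoT) and the GAD-7 row (BL, T1, T3/EoT) both carry a BL mark. They confirm the column alignment of the eC-SSRS row in Table 1-2.

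| Visit | Nominal day | eC-SSRS | Eligibility review | Relevant event |
|---|---|---|---|---|
| SCR-1 | -42 to -24 | yes | yes | withdrawal, if needed |
| SCR-2 | -10 | no | yes | screening PSG |
| BL | 1 | no | yes | GAD-7, randomization, first dose that evening |
| T1 | 29 (+7) | yes | no | Week 4 |
| T3/EoT | 85 (+7) | yes | no | Week 12 |

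**Step 2: order within SCR-1.** Section 8.2.2 requires device entries at a site visit to be made before any other study activity, and lists the eC-SSRS among the tablet instruments. The SCR-1 form therefore precedes a withdrawal made at that visit.

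**Step 3: count the days.** SAP 4.1.2 has no day 0, so day -k lies k days before day 1, and day d lies d - 1 days after it.

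- SCR-1 to first dose: 24 days (day -24) to 42 days (day -42).
- First dose to T1: 29 - 1 = 28 days to 36 - 1 = 35 days.
- SCR-1 form to next form: 24 + 28 = 52 days to 42 + 35 = 77 days.
- Share of that interval before the first dose: lowest 24/(24 + 35) = 40.7%, highest 42/(42 + 28) = 60.0%.
- Screening extended to 8 weeks (56 days): 56 + 28 = 84 days to 56 + 35 = 91 days, and more if extended further.

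These ranges use nominal visit days. Sections 1.1 and 5.5 allow added time for washout or delay, so 77 days is not an upper bound for the women in question.

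**Step 4: look for another scheduled suicidality question before dosing.** Exclusion 2 lets the investigator exclude on screening findings, including the eC-SSRS, but the only such result is the one from SCR-1. The GAD-7 at BL alerts the investigator at a score of 10 or more, but it measures anxiety. The single PHQ-9 item attached to it (SAP 4.4.4) asks about difficulty in functioning. None of these schedules a question on suicidal ideation or behaviour.

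**Step 5: how many women.** SAP Table 6-6 names eight relevant substances: citalopram, bupropion, venlafaxine, diazepam, clonazepam, alprazolam, gabapentin and topiramate. It gives no counts and does not separate use before the first dose from use on treatment, so no rate can be derived.

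**The case against.** **Eligibility is formally reviewed again.** A reader might infer that exclusion 15 is never revisited after SCR-1. The documents do not support that. The criteria are marked for review at SCR-2 and BL, both in person; exclusion 2 allows clinical judgement; and the GAD-7 alert prompts further evaluation. What stands is narrower: the later reviews have no new answers from the instrument that defines the criterion.

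**The analysis is little affected.** A reader might also infer that washout events will distort the comparison of treatment-emergent events. SAP 4.1.1.4 does provide that, where the first dose falls within the possible range, an "incomplete AE/CM start date will be imputed as the start of study treatment date". But this is a general worst-case rule that applies only to incomplete dates. An event with a full onset date before the first dose and no later worsening is not treatment-emergent under SAP 4.5.2. Allocation is randomized and double-blind, so washout effects fall on both arms equally in expectation, and the eC-SSRS table is descriptive. No bias between arms follows.

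**Reporting before dosing is not closed off.** Section 8.4.1 already takes procedure-related events as (S)AEs from consent, and protocol-directed withdrawal most naturally counts as such a procedure. A sentence saying so would be clarification. The limit that remains is that ideation nobody asks about may go unreported.

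**A simple repeat at BL could do harm.** The first eC-SSRS covers lifetime suicidality and later forms monitor prospectively. Under the default rule in SAP 4.1.2, the latest pre-dose form becomes the baseline. A short follow-up form could then displace the lifetime evaluation, and it may not span the 6 months that exclusion 15 asks about. This objection holds, and the remedy has to keep both forms.

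**Scale and version.** Antidepressants are among the treatments that Section 2.2 says guidelines recommend for sleep disturbance, so their use need not indicate depression. The protocol supplied is Amendment 1 (21 SEP 2023), while the SAP cites protocol Version 2.1 (06 FEB 2024). The word baseline in SAP 4.5.3.4 does not show at which visit the form is taken, so it cannot confirm that BL is still blank in that version.

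**Conclusion.** The gap is real in the supplied documents. For a woman withdrawn from prohibited psychotropics at SCR-1, exclusion 15 rests on a form completed before the withdrawal. No further eC-SSRS is scheduled until Week 4, 52 to 77 days later on nominal visit days, with 24 to 42 of those days before the first dose. The interval lengthens if screening is extended, and Section 5.5 does not add the form.

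This is a participant-safety improvement that should be made because it is cheap. It is not a defect in the primary estimand or in the randomized comparison. The conclusion rests on three things: the Amendment 1 schedule still applying, withdrawal happening at SCR-1 as Section 4.1 describes, and device entry coming first as Section 8.2.2 requires. The number of participants affected is unknown.

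**What to change.** **While enrolment is open**

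- Keep the SCR-1 eC-SSRS as the lifetime and 6-month evaluation.
- Add a follow-up eC-SSRS at BL before randomization, at minimum for participants who underwent washout or whose screening was extended under Section 5.5.
- Apply exclusion 15 to the two forms together.
- In SAP 4.5.3.4, name the SCR-1 form as the lifetime evaluation and the BL form as the immediate pre-treatment reference, so that the default baseline rule does not replace one with the other.

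The cost is one mark in the Schedule of Activities at a visit already held in person, on a tablet already at the site. It takes a few minutes per participant and may add a few screen failures.

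**If enrolment has closed**

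- Add the eC-SSRS to the SAP 4.5.3 count of baselines taken while using or washing out prohibited drugs.
- List the drug stop date beside any positive Week 4 form.

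This costs one table entry and one listing column.
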